RECIST	Response Evaluation Criteria in Solid Tumors
RM-NPC	recurrent/metastatic nasopharyngeal carcinoma
RP2D	recommended Phase 2 dose
SAE	serious adverse event
SAP	Statistical Analysis Plan
SD	stable disease
SI	Système International
SMC	Safety Monitoring Committee
TEAE	treatment-emergent adverse event
TESAE	treatment-emergent serious adverse event
WHODDE	World Health Organization Drug Dictionary Enhanced

1. INTRODUCTION

The purpose of this Statistical Analysis Plan (SAP) is to provide comprehensive and detailed descriptions of the methods and presentation of data analyses proposed for Viracta Therapeutics, Inc. Protocol VT3996-301 (An Open-Label, Multicenter Phase 1b/2 Study of Nanatinostat and Valganciclovir in Patients with Advanced Epstein-Barr Virus-Positive [EBV⁺] Solid Tumors and in Combination with Pembrolizumab in Patients with Recurrent/Metastatic Nasopharyngeal Carcinoma). Descriptions of planned analyses are provided in order to avoid post hoc decisions that may affect the interpretation of the statistical analysis. The statistical methods applied in the design and planned analyses of this study are consistent with the International Council for Harmonisation (ICH) guidelines *Statistical Principles for Clinical Trials (E9)* (1998) and *Statistical Principles for Clinical Trials: Addendum: Estimands and Sensitivity Analysis in Clinical Trials (E9[R1])* ([2021](#)).

This SAP will be finalized prior to data analysis and before database lock to provide comprehensive details of the tables, figures, and listings to be presented in the Clinical Study Report (CSR). Any changes between the statistical methods provided in the clinical study protocol and this SAP will be explained herein; any changes or deviations from this SAP relative to the final analysis will be fully documented in the CSR. Minor changes or deviations from the templates for tables, figures, and listings need not be documented in the CSR.

2. STUDY OBJECTIVES

2.1 Primary Study Objectives

The primary objectives of this study include the following:

- Phase 1b: To determine the recommended Phase 2 dose (RP2D) of nanatinostat in combination with valganciclovir; and
- Phase 2:
 - To confirm the RP2D of nanatinostat in combination with valganciclovir;
 - To estimate the objective response rate (ORR) of nanatinostat and valganciclovir alone and in combination with pembrolizumab.

2.2 Secondary Study Objectives

The secondary objectives of this study include the following:

- To characterize the safety and tolerability of nanatinostat and valganciclovir alone and in combination with pembrolizumab;
- To characterize the pharmacokinetic (PK) properties of nanatinostat in combination with valganciclovir; and

- To evaluate additional preliminary efficacy parameters of nanatinostat and valganciclovir alone and in combination with pembrolizumab.

2.3 Exploratory Study Objective

The exploratory objectives of this study include the following:

- Evaluate potential biomarkers of activity of nanatinostat and valganciclovir alone and in combination with pembrolizumab; and
- Evaluate the safety, tolerability, PK, pharmacodynamic (PD), and antitumor activity of nanatinostat in combination with valganciclovir in patients with non-NPC EBV⁺ solid tumors.

3. INVESTIGATIONAL PLAN

3.1 Overall Study Design

This is a Phase 1b/2, open-label, multicenter study designed to evaluate the safety and preliminary efficacy of oral nanatinostat and valganciclovir alone and in combination with IV pembrolizumab in patients with EBV⁺ recurrent/metastatic nasopharyngeal carcinoma (RM-NPC). The safety and tolerability of study drug treatments will be evaluated by means of adverse event (AE) reports, laboratory safety evaluations, vital sign measurements, 12-lead resting electrocardiograms (ECGs), physical examinations, and Eastern Cooperative Oncology Group (ECOG) performance status. The efficacy of study drug treatments will be evaluated for Phase 2 patients per tumor response measurements. Pharmacokinetic and pharmacodynamic assessments are also planned.

Phase 1b

A traditional 3+3 dose escalation design will be used to determine the RP2D of nanatinostat and valganciclovir; approximately 27 to 60 patients with RM-NPC will be enrolled; cohorts of 3 to 6 patients with RM-NPC will be enrolled sequentially at escalating nanatinostat doses starting with 20 mg daily on Days 1 to 4 per week (intermittent dosing) with valganciclovir 900 mg daily. Any patients in screening when the last patient is enrolled in a cohort may also be enrolled if eligible. Dose escalation of nanatinostat will continue as described below until the RP2D is identified:

- Total daily nanatinostat dose of 30 and 40 mg daily administered as a single dose on Days 1 to 4 per week with valganciclovir 900 mg once daily; or
- Divided nanatinostat dose twice daily on Days 1 to 4 per week with valganciclovir 900 mg once daily or valganciclovir 900 mg twice daily for 21 days followed by a subsequent dose reduction to 900 mg once daily; or
- Split daily dose of nanatinostat starting at 20 mg with valganciclovir 450 mg twice daily, 4 hours apart on Days 1 to 7 per week.

Because plasma EBV deoxyribonucleic acid (DNA) levels correlate closely together with the presence of disease and response to therapy in RM-NPC, these data will be considered together with safety data in the selection of the RP2D.

Phase 2

Following dose escalation, Phase 2 will begin with a dose optimization cohort to assess the safety, tolerability, PK, PD, and antitumor activity of nanatinostat and valganciclovir and to confirm its RP2D in patients with RM-NPC.

Patients will be randomly assigned 1:1 to each treatment group (up to 20 patients in each treatment group for approximately 40 patients total) during the dose optimization cohort period. The starting doses of nanatinostat for the treatment groups will be the RP2D and another dose level below the RP2D (<RP2D) plus valganciclovir 450 mg twice daily, based on the Safety Monitoring Committee's (SMC's) review of the totality of the data from the previous Phase 1b cohorts. After the nanatinostat and valganciclovir RP2D is confirmed by the SMC based on the results of the dose optimization cohorts, up to 60 patients with RM-NPC will be randomly assigned 1:1 to receive that RP2D of nanatinostat and valganciclovir with or without concomitant pembrolizumab to assess the preliminary antitumor activity, safety, and tolerability of each regimen in the Phase 2 dose expansion period. Randomization will be stratified by prior anti programmed cell death protein 1(PD-1) treatment exposure.

Pembrolizumab will be dosed at 200 mg intravenous(ly) (IV) every 3 weeks for those patients randomly assigned to the nanatinostat, valganciclovir, and pembrolizumab group. An early safety analysis will be performed after the first 6 patients are randomized to receive nanatinostat and valganciclovir in combination with pembrolizumab and have been followed for at least 2 cycles (7 weeks) of treatment as described in Section 5.5.3.3 of the clinical study protocol.

[figure not shown]
In addition, up to 10 patients with advanced EBV⁺ non-NPC solid tumors (gastric cancer, lymphoepithelioma-like carcinoma, and leiomyosarcoma) will be enrolled in a Phase 1b exploratory proof-of-concept cohort to characterize the safety and PK of the nanatinostat and valganciclovir combination in other solid tumors. Enrollment in this proof-of-concept cohort will begin when the appropriate RP2D for this population is determined in consultation with the SMC, while enrollment in the proof-of-concept cohort may be stopped before 10 patients are treated if a) evidence of safety or tolerability issues arise or b) Phase 2 of the study completes enrollment.

All patients will be monitored at weekly intervals for the first 6 weeks, and then at 3-week intervals thereafter starting at Week 8. Tumor responses will be assessed at Week 8 and then every 6 weeks for the first 26 weeks (6 months) and every 12 weeks thereafter by the Investigator per Response Evaluation Criteria in Solid Tumors version 1.1 (RECIST v1.1). A scan to confirm an unconfirmed partial response (PR) or unconfirmed complete response (CR) ≥ 4 weeks later may also be performed.

Patients will continue to receive study drug until the development of progressive disease (per Investigator assessment), unacceptable toxicity, withdrawal of consent, Investigator's discretion, initiation of new antineoplastic therapy, or study termination by the Sponsor. The maximum treatment with pembrolizumab is 24 months.

The study design is summarized in [Figure 1](#) on the next page.

Figure 1 Study Design

CT = computed tomography; DLT = dose-limiting toxicity; EBV = Epstein-Barr virus; MRI = magnetic resonance imaging; NPC = nasopharyngeal carcinoma; RECIST v 1.1 = Response Evaluation Criteria in Solid Tumors Version 1.1; RM = recurrent and/or metastatic; RP2D = recommended Phase 2 dose; SDD = split daily dose

[1] Patients must have a histologically confirmed diagnosis of EBV⁺ recurrent or metastatic NPC or other solid tumor type and received previous systemic therapy for their cancer; have measurable disease determined by magnetic resonance imaging (MRI) or computed tomography with contrast at screening; and have adequate bone marrow, liver, and renal function.

[2] Starting nanatinostat dose is 20 mg once daily on Days 1 to 4 per week with valganciclovir 900 mg daily. Dose escalation of nanatinostat will continue with i) a total daily dose of 30 and 40 mg daily administered as a single dose on Days 1 to 4 per week with valganciclovir 900 mg once daily, ii) as a divided nanatinostat dose twice daily on Days 1 to 4 per week with valganciclovir 900 mg once daily or twice daily for 21 days followed by a subsequent dose reduction to 900 mg once daily, then iii) as a SDD of nanatinostat starting at 20 mg and valganciclovir at 450 mg twice daily 4 hours apart on Days 1 to 7 per week until the RP2D is determined.

^[3] EBV⁺ non-NPC solid tumors may include gastric cancer, lymphoepithelioma-like carcinoma, and leiomyosarcoma - dosing regimen for the proof-of-concept cohorts will be determined on data collected and analyzed at or after the RP2D from Phase 1b is determined.

^[4] Pembrolizumab: Standard 200 mg IV every 3 weeks.

^[5] Long-term follow-up assessments include tumor evaluation and EBV DNA viral levels (for patients who discontinued treatment for reasons other than disease progression), survival assessment until lost to follow-up, death, or withdrawal of consent, and subsequent anti-neoplastic therapies.

Screening Period

At screening, the patient will provide a signed informed consent form prior to any study-related activities. Collection and shipment of a formalin-fixed paraffin-embedded (FFPE) tumor sample (archived tissue or new biopsy specimen) to the central pathology laboratory should occur as early as possible, and no later than 8 weeks following Cycle 1 Day 1. The tumor sample will be used for central confirmation of EBV status and exploratory assessments as described in Table 3 of the clinical study protocol. For tumor specimens >2 years old, the Sponsor's Medical Monitor should be consulted to discuss eligibility. Additional screening evaluations must be performed within 28 days or 21 days before treatment start (Cycle 1 Day 1) as defined in the Schedule of Events (Table 11). At the time of screening, male patients should be informed about their options to store germ cells in advance of study treatment.

Treatment Period

The treatment period will begin on Cycle 1 Day 1. Cycle 1 will be 28 days; all subsequent cycles will be 21 days. Patients will be treated until unacceptable toxicity, death, progressive disease, treatment discontinuation at the discretion of the Investigator, or withdrawal of consent (maximum treatment duration with pembrolizumab is 24 months). Patients with first evidence of progressive disease and no clinical deterioration may continue study treatment until a repeat scan within 4 to 6 weeks confirms disease progression. To account for atypical disease response to immune therapy, Investigators are encouraged to follow immune-modified Response Evaluation Criteria in Solid Tumors (iRECIST) criteria (criteria based on RECIST v 1.1 for response and progressive disease, but adapted to account for the tumor response seen with immunotherapeutic drugs as described in Appendix 3 of the clinical study protocol) for treatment decision making, including confirmation of unconfirmed progressive disease with additional imaging.

Safety Follow-Up Period

Upon discontinuation of the protocol-specified treatments, patients will enter the Follow-up period. All patients must complete a safety follow-up assessment at 30 and 90 days after receiving their last dose of study drug. All AEs for patients treated with nanatinostat, valganciclovir, and pembrolizumab and only serious AEs (SAEs) for all other patients will be collected up to and including 90 days after the last dose of study treatment or until the start of a new antineoplastic therapy, whichever occurs first. The 90-day safety follow-up assessment may coincide with the first Long-Term Follow-Up visit.

Information related to concomitant medications used to treat AEs and any anti-neoplastic therapies taken following permanent discontinuation of study treatment will be collected for 90 days after the last dose of study treatment for all patients. If a new

antineoplastic treatment is initiated before the 30-day safety evaluation, safety follow-up will occur immediately before starting the new treatment. If a patient withdraws consent after the End of Treatment (EOT) visit, but prior to the 30-day safety evaluation, safety data should be collected on the patient up to the date of consent withdrawal.

Long-Term Follow-Up Visit

All patients enrolled in the study will be followed for survival every 12 weeks (or more frequently if a survival update is required for safety or regulatory reasons) until withdrawal of consent, death, loss to follow-up, completion of 3 years of follow-up, completion of 1 year after the last patient discontinues study treatment, or the study is terminated by the Sponsor, whichever occurs first. Patients will also be followed during this period for disease progression (for those who discontinued treatment for reasons other than disease progression), overall survival, and subsequent anti-neoplastic therapies, including response.

Patients enrolled in the study who discontinue study treatment for any reason other than disease progression will have a tumor assessment every 12 weeks (± 7 days), up to 1 year from the date of the last dose of study treatment, until disease progression, the initiation of subsequent anti-cancer therapies, withdrawal of consent, loss to follow up, or end of the study, whichever occurs first. Any newly started anti-neoplastic therapies should be recorded on the *Antineoplastic Therapy Since Discontinuation* electronic case report form (eCRF) page.

End of Study

The end of the study occurs when all patients have either progressed, discontinued, died, become lost to follow-up, or have maintained a complete response, partial response, or stable disease for at least 3 years, or when the trial is terminated by the Sponsor. Patients continuing to derive benefit from study treatment in the opinion of the Investigator at the end of the study may be able to continue receiving study treatment on an individual basis (e.g., by separate protocol or post-trial access plan) with Sponsor's Medical Monitor approval.

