CR: Disappearance of all non-target lesions and normalization of tumor marker levels. All lymph nodes must be non-pathological in size (< 10 mm in the short axis).

Non-CR/non-PD: Persistence of 1 or more non-target lesions or tumor marker levels maintained above normal limits.

PD: Unequivocal progression of existing non-target lesions or the appearance of 1 or more new lesions.

Overall Response

The following table shows the criteria for the assessment of overall response at each time point for subjects who have measurable lesions at baseline.

Evaluation of Overall Response at Each Time Point

Target Lesions	Non-Target Lesions	New Lesions	Overall Response
CR	CR	No	CR
CR	Non-CR/non-PD	No	PR
CR	Not evaluated	No	PR
PR	Non-PD/not evaluated	No	PR
SD	Non-PD/not evaluated	No	SD
NE	Non-PD	No	NE
PD	Any	Yes or no	PD
Any	PD	Yes or no	PD
Any	Any	Yes	PD

Source: RECIST version 1.1 criteria.

Abbreviations: CR = complete response; NE = not evaluable; PD = progressive disease; PR = partial response; RECIST = Response Evaluation Criteria in Solid Tumors; SD = stable disease.

Best Overall Response

Best overall response (BOR) in this study is defined as the BOR across all time points, eg, a subject who has SD at first assessment, partial response at second assessment, and PD at last assessment has a best overall assessment of PR. If SD is assessed as the BOR, it must also meet the SD criteria at least once after study entry at 6 weeks or longer from baseline. If SD is the best time point response and the minimum time requirement is not met, the subject's best response will depend on subsequent assessments eg, a subject who has SD at first assessment and PD at second assessment and does not meet the minimum duration for SD, will have a best overall assessment of PD. The same subject lost to follow-up after the first SD assessment would be considered unevaluable.

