3.4 Efficacy and Safety Variables

3.4.1 *Efficacy Variables*

3.4.1.1 *Primary Efficacy Variable*

Tumor responses will be assessed by the Investigator per RECIST v1.1 using MRI or CT scan assessments. For patients receiving pembrolizumab, tumor responses will also be assessed per immunologic RECIST (iRECIST). Tumor imaging will be repeated to confirm disease progression using iRECIST.

The primary efficacy endpoint is ORR, defined as the percentage of patients with a CR or PR as assessed by RECIST v1.1 within the first 26 weeks (6 months) of treatment. The ORR will also be calculated using iRECIST for patients receiving pembrolizumab.

3.4.1.2 *Secondary Efficacy Variables*

Secondary efficacy endpoints include the following:

- Time to response (TTR) – defined as the interval from the start of study drug treatment to the date of first documented CR or PR per RECIST or iRECIST.
- Duration of response (DOR) – defined as the interval of time from the date of first observed CR or PR to the date of documented disease progression or death due to any cause, whichever occurs first. Dates of progression and censoring will be determined as described in [Section 4.5.5.2](#);
- Disease control rate (DCR) – defined as the percentage of patients having a CR, PR, or stable disease (SD) at any time during treatment;
- Progression-free survival (PFS) – defined as the interval of time from the start of study drug treatment to the date of first documented disease progression, initiation of new antineoplastic therapy, withdrawal of consent, loss to follow-up, or death due to any cause, whichever occurs first. Dates of progression and censoring will be determined as described in [Section 4.5.5.2](#); and
- Overall survival (OS) – defined as the interval of time from the start of study drug treatment to the date of death due to any cause. Patients without

documentation of death at the time of analysis will be censored at the date the patient was last known to be alive.

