4.5.3 Primary Efficacy Endpoint Analysis Methods

Counts and percentages for each tumor response category assessed by the Investigator per RECIST v1.1 will be presented by dosing regimen. Separate summaries will also be produced by prior anti-PD-1 treatment exposure. Non-evaluable patients are considered non-responders and will be included in the denominator. ORR estimates, from the first post-baseline assessment, with corresponding binomial 95% confidence intervals using the Clopper-Pearson Exact method will also be presented.

For patients receiving pembrolizumab, the analysis will be repeated using iRECIST.

Results from tumor assessments will be provided in separate listings.

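### ORR counts a response seen on one unblinded investigator-read scan; a supportive confirmed ORR should be reported beside it, and its scan window stated clearly

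*SAP*

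**What the plan says.** SAP 3.4.1.1 defines the primary efficacy endpoint as the percentage of patients with a CR or PR "as assessed by RECIST v1.1 within the first 26 weeks (6 months) of treatment". SAP 4.5.3 has the Investigator as reader, and SAP 3.3.3 confirms that the study is open-label.

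On confirmation, SAP 3.1 says: "A scan to confirm an unconfirmed partial response (PR) or unconfirmed complete response (CR) ≥ 4 weeks later may also be performed". The protocol is equally permissive in the synopsis, Sections 3.1, 3.3 and 7.4.1.2, and Table 11 footnote o. No section requires a response to be repeated.

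Protocol Appendix 3 settles how a lone response is scored. It says "Best overall response (BOR) in this study is defined as the BOR across all time points", and its example is that "a subject who has SD at first assessment, partial response at second assessment, and PD at last assessment has a best overall assessment of PR".

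SAP 4.5.3 adds: "ORR estimates, from the first post-baseline assessment, with corresponding binomial 95% confidence intervals using the Clopper-Pearson Exact method will also be presented". The only other efficacy set is the modified Intent-to-Treat Population (SAP 4.5.1 and 4.5.5.6). Neither a confirmed ORR nor a central read of scans is planned.

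SAP 4.8 records that the study did not proceed to Phase 2, that Phase 2 analyses will not be performed, and that ORR was added as a primary efficacy endpoint for Phase 1b.

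**The concern.** The plan separates unconfirmed from confirmed responses in its scan schedule, and Protocol Appendix 4 sets detailed rules for confirming progression under iRECIST. Response has no such rule. One measurement that falls by chance below the 30% threshold makes a patient a responder, and a later progression does not undo it. If ORR is taken over all scans to Week 26, each further scan is another chance for this to happen.

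The Phase 1b groups are small. In cohorts of 3 to 6 patients (SAP 3.1), one responder moves the cohort's ORR by 1/6 = 17 to 1/3 = 33 percentage points. Time to response and duration of response also start at the first CR or PR (SAP 3.4.1.2), so a spurious response carries into both.

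**Working it through.** **1. The plan's own figure.** SAP 4.7 says that with an ORR near 25% and n = 30, the 95% interval excludes 10%. Two-sided Clopper-Pearson lower limits are:

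- 7/30 (23.3%): 9.93%
- 7.5/30 (25%, interpolated): 11.1%
- 8/30 (26.7%): 12.3%

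The statement reproduces, narrowly: one responder fewer than 8 brings 10% back inside. This shows how much one response can weigh, but it concerns Phase 2, which will not be analysed. It is not a Phase 1b criterion.

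**2. Can scheduled scans confirm?** Scans fall at Weeks 8, 14, 20 and 26, then every 12 weeks (SAP 3.1). They are counted in calendar days (Protocol 7.4.1.2) with a window of ±7 days (Protocol Section 6). The smallest gap through Week 26 is 42 − 7 − 7 = 28 days, which meets the 4-week condition. A response first seen at Week 26 is next scanned at Week 38.

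**3. How many non-responders could be miscounted?** The documents give no false-response rate. Assume a probability f per scan of a true non-responder, independent between scans, with f = 2% to 5%.

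- At least one false response in k scans: 1 − (1 − f)^k
- Two consecutive false responses in two scans: f²
- Two consecutive false responses in four scans: 3f² − 2f³

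| Scans | f | At least one | Two consecutive |
|---|---|---|---|
| 2 | 2% | 1 − 0.98² = 3.96% | 0.02² = 0.04% |
| 2 | 5% | 1 − 0.95² = 9.75% | 0.05² = 0.25% |
| 4 | 2% | 1 − 0.98⁴ = 7.8% | 0.001200 − 0.000016 = 0.12% |
| 4 | 5% | 1 − 0.95⁴ = 18.5% | 0.00750 − 0.00025 = 0.73% |

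These are shares of non-responders. The upward shift in expected ORR is (1 − true ORR) times the value.

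**4. The wording of the estimate.** SAP 4.5.3 takes ORR from the first post-baseline assessment. Read as the Week 8 scan alone, there is one chance and the false share is f itself, 2-5%. Read as best response from that scan onward, the table applies. SAP 3.4.1.1, with its 26-week window, supports the second reading. A single scan suffices under either.

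**The case against.** The strongest reply is that little rests on this now. The study is descriptive and compares no regimens formally (SAP 4.1.1), and cohort intervals are very wide whatever the rule: 0.4% to 64% for 1/6 and 0.8% to 91% for 1/3. Tumor assessments and derived efficacy measures will be listed (SAP 4.5.3 and 4.5.4). A PR followed by PD would appear as a short duration of response, so a reader can trace each responder. This stands as a partial check. It does not give a defined confirmed rate, and readers would have to build one themselves under rules of their own.

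Second, the four-scan figure is an upper case, because treatment generally stops at progression. Protocol 1.2.1 cites median PFS of 1.9 and 2.8 months in two PD-1 inhibitor studies. With exponential PFS and a Week 8 scan for everyone, expected scans are 1 + S(8) + S(14) + S(20), where S(w) is the proportion progression-free at week w. That is 1 + 0.51 + 0.31 + 0.19 = 2.0 and 1 + 0.63 + 0.45 + 0.32 = 2.4. This stands, and is why the two-scan case is given. The same section also cites 6.5 months for pembrolizumab, so two scans is not a ceiling.

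Third, two readings by one unblinded investigator share the baseline measurement and any habit of reading. Repetition reduces random error, not consistent bias, so the two-consecutive column is a best case. This also stands.

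Fourth, some responses may have no second scan: those first seen at Week 26, those at sites limited to 12-weekly imaging (Protocol 7.4.1.2), and those of patients moved from long-term follow-up to End of Study (SAP 4.8). Without a rule, a confirmed ORR would mix failure to repeat with failure to rescan. This bears on how the row is specified, not on whether to add it.

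**Conclusion.** The point holds as a recommendation for a supportive analysis. As written, one unblinded investigator reading is enough to make a responder on a primary Phase 1b endpoint, which can bias ORR upward. The size, 4-10% of non-responders with two scans and 8-19% with four, depends wholly on the assumed 2-5% per scan and on independent errors. It is not an estimate from trial data.

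Three stronger readings are not supported:

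- A reader might infer that false responses could carry the trial past a 10% floor. That floor and n = 30 belong to the Phase 2 sample-size text, and no floor is set for Phase 1b.
- A reader might infer that the planned ORR is inflated relative to the 20-30% benchmarks. The documents do not say whether those are confirmed rates.
- A reader might infer that a confirmed ORR is free of bias. It can miss true responders who were not rescanned or who progressed before the next scan, and it leaves consistent reading bias in place. This is why both rates should be shown.

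**What to change.** In SAP 4.5.3:

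1. State that ORR is the best response from the first post-baseline assessment through Week 26, so that it agrees with SAP 3.4.1.1.
2. Beside it, report a supportive confirmed ORR with a Clopper-Pearson interval. A confirmed response is a CR or PR repeated on the next evaluable assessment at least 4 weeks later, using scheduled or optional scans. Let the next scan after Week 26 confirm a response first seen at Week 26.
3. Keep responders with no later scan in the denominator as not confirmed. Show them on a separate line, such as *unconfirmed, no later scan*, apart from responses that failed to repeat.

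If ORR is set against the literature, say which version is being compared.

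The cost is an additional derivation and a few table lines, with no added scans and no change to the planned ORR. The confirmed rate will be somewhat lower. Some responses will be impossible to confirm because of 12-weekly imaging or early closure of follow-up. SAP Section 1 has the plan finalized before database lock and later changes documented in the clinical study report, so there is a route in either case.
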